#### 4.1.2.2 Pembrolizumab (MK-3475) Preclinical and Clinical Trials

Efficacy studies in mouse models have shown that administration of antibodies blocking PD-1/PD-L1 interaction, either as a mono-therapy or in combination with other treatment modalities, enhances infiltration of tumor-specific CD8+ T-cells and leads ultimately to tumor rejection. Anti-mouse PD-1 or anti-mouse PD-L1 antibodies have demonstrated anti-tumor responses as a monotherapy in models of squamous cell carcinoma, pancreatic carcinoma, melanoma and colorectal carcinoma. Blockade of the PD-1 pathway effectively

[figure not shown]
promoted CD8+ T-cell infiltration into the tumor and the presence of IFN- $\gamma$ , granzyme B and perforin, indicating that the mechanism of action involved local infiltration and activation of effector T-cell function in vivo [40], [46], [45], [47]. Experiments have confirmed the in vivo efficacy of PD-1 blockade as a mono-therapy as well as in combination with chemotherapy in syngeneic mouse tumor models (see the IB).

Pembrolizumab [KEYTRUDA® (US); previously known as lambrolizumab, MK-3475 and SCH 9000475] is a potent and highly selective humanized monoclonal antibody (mAb) of the IgG4/kappa isotype designed to directly block the interaction between PD-1 and its ligands, PD-L1 and PD-L2. KEYTRUDA® (pembrolizumab) is indicated for the treatment of patients across a number of indications. For more details on specific indications refer to the IB.

#### **4.1.2.3 MK-1248 with Pembrolizumab Combination Preclinical Trials**

As MK-1248 acts to stimulate effector immune cells while pembrolizumab acts to prevent immune suppression in tumors, it is conceivable that a combination of MK-1248 and pembrolizumab may result in further stimulation of the immune system against malignant disease and thereby greater anti-tumor efficacy. This hypothesis was tested in preclinical models, the results of which provide support for the proposed clinical trial.

Studies have been conducted in the CT26 syngeneic mouse tumor model to assess the anti-tumor efficacy of treatment with mDTA-1 IgG1 (mouse surrogate for MK-1248) in combination with muDX400 (mouse surrogate for pembrolizumab). mDTA-1 IgG1 or muDX400 were administered either as monotherapy or in combination twice with a seven day interval at previously determined maximally effective monotherapeutic doses. Administration of mDTA-1 IgG1 in combination with muDX400 resulted in greater anti-tumor efficacy than administration of either antibody alone ([Figure 4](#)).

The CT26 colon adenocarcinoma cells were implanted into immunocompetent BALB/cAnN mice subcutaneously. Animals were assigned into treatment groups when the tumor volume ranged from approximately 77 to 115 mm^3. mIgG1 isotype control monoclonal antibody (mIgG1) was administered SC or IP on Days 0 and 7. muDX400 alone was administered IP on Days 0 and 7. mDTA-1 IgG1 alone was administered SC on Day 0. mDTA-1 IgG1 was administered SC in combination with muDX400 administered IP on Days 0 and 7. In panel A, mean group tumor volumes ( $\pm$  standard error of the mean) are presented. Statistical comparisons of tumor volume between groups are presented in panel B. In panel B, individual animal tumor volumes on Day 35 are presented. Open symbols are measured values from Day 35; solid symbols are censored data (final measurement taken before Day 35). In panel C, animal survival curves are presented. Comparison of animal survival between groups was conducted using Log-rank with Mantel-Cox test analysis. Comparisons with significant differences are shown in panel C. Tumor volumes presented are from Study 14-M320-6565. There were 10 animals in each group.

Figure 4 Efficacy of Combination Treatment with mDTA-1 IgG1 and muDX400 in Established Syngeneic Mouse Tumor Model

### **4.1.3 Ongoing Clinical Trials**

#### **4.1.3.1 MK-1248 Ongoing Clinical Trials**

This is the first clinical trial with MK-1248. A Phase 1 clinical trial with MK-4166, an anti-GTIR humanized mAB of the IgG1 class, is ongoing as described previously in Section 4.1.1.1.

#### **4.1.3.2 Pembrolizumab Ongoing Clinical Trials**

Ongoing clinical trials with pembrolizumab are being conducted in multiple solid tumors, including melanoma, non-small cell lung cancer, head and neck cancer, triple negative breast cancer, gastric cancer, and bladder cancer, as well as hematological malignancies. In addition, multiple combinations with pembrolizumab are also being investigated, including the combination of pembrolizumab with MK-4166 (anti-GITR). For trial details please refer to the pembrolizumab IB.

### **4.1.4 Information on Other Trial-Related Therapy**

No comparators are proposed for this trial.

## **4.2 Rationale**

### **4.2.1 Rationale for the Trial and Selected Subject Population**

MK-1248 is being developed for treatment of solid tumors. This trial is the first-in-human trial designed to assess the safety, tolerability, pharmacokinetics and pharmacodynamics of escalating doses of MK-1248 alone and in combination with pembrolizumab in subjects with advanced solid tumors that have failed standard therapy. The effect of MK-1248 on tumor size will also be explored. The trial will enroll subjects with solid tumors without regard to specific tumor type.

### **4.2.2 Rationale for Dose Selection/Regimen/Modification**

MK-1248 and MK-4166 are both monoclonal antibodies with similar binding to the GITR receptor and different Fc regions; MK-4166 has a functional IgG1 domain while MK-1248 utilizes an IgG4 framework. Therefore, the dose regimen proposed for this first-in-human trial of MK-1248 is based on the experience in the MK-4166 first-in-human trial. Specifically, doses of 0.0015 to 10 mg have been administered to single-dose cohorts of subjects in MK-4166 PN 001 and no DLTs have been reported in these subjects. A dose of 30 mg MK-4166 was administered to 3 subjects, with 1 subject reporting a DLT. This DLT was a Grade 3 Indiana Pouch perforation reported in a subject with metastatic urethral cancer in which the investigator determined the event to be possibly related to study drug because of the low incidence of spontaneous perforation and no obvious explanation for the event. As of 01-Mar-2017, data are available for a total of 81 patients: 45 patients treated with MK-4166 monotherapy and 36 patients treated with MK-4166 in combination with pembrolizumab. Dose escalation has reached 670 mg in the monotherapy treatment arm and 480 mg in the combination treatment arm; dose escalation is continuing per protocol.

#### 4.2.2.1 Starting Dose for This Trial

The starting dose of MK-1248 for this trial was determined by the following criteria:

- 1) MK-1248 has similar GITR binding epitope to MK-4166 while due to its IgG4 domain MK-1248 is predicted to have lesser Fc-related activity compared to the MK-4166, with its functional IgG1 domain.
- 2) Preclinically, cytokine release activity representing the minimum active biologic activity for MK-1248 is similar to MK-4166 (see below).
- 3) MK-4166 has been administered to subjects at doses ranging from 0.0015 mg to 10 mg without any DLTs. One DLT has been reported at a dose of 30 mg and dose escalation is ongoing.
- 4) The GITR receptor binding pharmacodynamic assay utilized in the MK-4166 protocol indicates that saturation of GITR receptors in the periphery approaches saturation as doses of 0.37 mg and higher.

Therefore, the starting dose of MK-1248 in this trial is planned to be 0.12 mg. The dose of 0.12 mg MK-1248 was chosen because safety data from the closely related MK-4166 molecule is available as doses approximately 100-fold higher than the 0.12 mg dose (i.e. at 10 mg MK-4166) without DLTs. Furthermore, while a starting dose of 0.12 mg is anticipated to have some GITR-binding pharmacodynamic activity, it is expected to be below the corresponding dose of MK-4166 at which full saturation of peripheral GITR receptors was approached (0.37 mg MK-4166).

Cynomolgus monkeys were used for studies of PK and GITR engagement as a bridging species to human administration. Cynomolgus monkeys were chosen as the relevant pharmacological species for the conduct of preclinical safety studies since MK-1248 binds to and co-activates cynomolgus monkey GITR with similar affinity and potency to that of human GITR. A broad survey of tissues from normal human and cynomolgus monkey demonstrated that GITR is expressed at low levels primarily on lymphoid cells in the blood and in lymphoid tissues in both species. In the blood, GITR expression on T-cells is comparable. However, a higher percentage of GITR-positive NK T-cells is present in cynomolgus monkey blood relative to human, and a large but variable percentage of GITR-positive NK cells is present in human while none are present in cynomolgus monkey blood. Non-linear PK properties were observed in cynomolgus monkeys at lower doses (0.0005 – 3 mg/kg). In line with changes in serum concentration-time profiles for MK-1248, a dose-dependent effect on GITR engagement in blood, as measured by a receptor (GITR) availability assay (RA assay described in IB), was observed in monkeys. Relationships between receptor (GITR) availability and MK-1248 serum concentrations were described by an inhibitory  $E_{max}$  model, which provided a preliminary estimate of a potency value ( $EC_{50} \approx 6 \text{ ng/ml}$ ) for blood GITR engagement. It should be noted that MK-4166 has a similar estimated potency value in this same model.

GITR+ T-cells in blood were evaluated for MK-1248 binding in cancer patients, normal healthy volunteers and Cynomolgus monkeys. Results from this experiment showed comparable binding potency and maximum binding capacity between humans and cynomolgus monkeys under the in vitro experimental conditions employed.

#### 4.2.2.2 Rationale for Pembrolizumab Dose

The planned dose of pembrolizumab for this study is 200 mg given once every 3 weeks. Based on the totality of data generated in the Keytruda development program, 200 mg given once every 3 weeks is the appropriate dose of pembrolizumab across all indications and regardless of tumor type. As outlined below, this dose is justified by:

- Clinical data from 8 randomized studies demonstrating flat dose-efficacy and exposure-efficacy relationships from doses of 2 mg/kg given once every 3 weeks to 10 mg/kg given once every 2 weeks;
- Clinical data showing meaningful improvement in benefit-risk including overall survival at 200 mg given once every 3 weeks across multiple indications; and
- Pharmacology data showing full target saturation in both systemic circulation (inferred from PK data) and tumor (inferred from physiologically-based PK analysis) at 200 mg given once every 3 weeks.

Among the 8 randomized dose-comparison studies, a total of 2262 subjects with either melanoma or non-small cell lung cancer were enrolled, covering different disease settings (i.e., treatment-naïve, previously treated, PD-L1-enriched, and all-comers) and different treatment settings (i.e., monotherapy and in combination with chemotherapy). Five studies compared 2 mg/kg given once every 3 weeks with 10 mg/kg given once every 3 weeks (KN001 B2, KN001 D, KN002, KN010, and KN021), and 3 studies compared 10 mg/kg given once every 3 weeks with 10 mg/kg given once every 2 weeks (KN001 B3, KN001 F2, and KN006). All of these studies demonstrated flat dose-response and exposure-response relationships across the doses studied representing an approximate 5-fold to 7.5-fold difference in exposure. The 2-mg/kg (or 200-mg fixed dose) given once every 3 weeks provided similar responses to the highest doses studied. Subsequently, flat dose-response and exposure-response relationships were also observed in other tumor types including head and neck cancer, bladder cancer, gastric cancer, and classical Hodgkin's lymphoma, confirming 200 mg given once every 3 weeks as the appropriate dose independent of the tumor type. These findings are consistent with the mechanism of action of pembrolizumab, which acts by interaction with immune cells, and not by direct binding to cancer cells.

Additionally, pharmacology data clearly show target saturation at 200 mg given once every 3 weeks. First, PK data in KN001 evaluating target-mediated drug disposition conclusively demonstrated saturation of PD-1 in systemic circulation at doses much lower than 200 mg given once every 3 weeks. Second, a physiologically-based PK analysis was conducted to predict tumor PD-1 saturation over a wide range of tumor penetration and PD-1 expressions. This evaluation concluded that pembrolizumab at 200 mg given once every 3 weeks achieves full PD-1 saturation in both blood and tumor.

Finally, population PK analysis of pembrolizumab which characterized the influence of body weight and other subject covariates on exposure, has shown that fixed dosing provides similar control of PK variability as weight-based dosing, with considerable overlap in the distribution of exposures from the 200-mg given once every 3 weeks dose and the 2-mg/kg given once every 3 weeks dose. Supported by these PK characteristics, and given that fixed dose has advantages of reduced dosing complexity and reduced potential of dosing errors, the

200-mg given once every 3 weeks fixed dose was selected for evaluation across all pembrolizumab protocols.

No dose reduction is allowed for pembrolizumab in this study.

#### **4.2.2.3 Maximum Dose/Exposure for This Trial**

Data from mouse efficacy studies and predictions of human target engagement suggest a human efficacious dose in the range of 60 mg to 330 mg for MK-1248. Although dose escalations will depend on adverse events, a potential dose up to 900 mg is planned. While the maximum clinical dose to be evaluated in this trial is 900 mg, studies in the appropriate safety species (cynomolgus monkey) showed no adverse effects at doses where the  $C_{max}$  and AUC values were twenty-fold and five-fold higher, respectively, relative to the predicted human exposure.

#### **4.2.2.4 Rationale for Dose Interval and Trial Design**

##### **4.2.2.4.1 MK-1248 Monotherapy**

Maximal efficacy was achieved in mouse preclinical studies using 3 mg/kg doses. In the rapidly progressing syngeneic tumor models, no improvement in efficacy was observed with weekly dosing (see IB). Because preclinical data suggests that long-term chronic dosing may not be necessary for full efficacy, we plan a limited number of MK-1248 administrations. A single first dose will be followed by a 3-week (DLT) observation period during which time subjects will be monitored for toxicity (including signs of systemic cytokine release) and target engagement monitored by receptor availability. In the absence of limiting safety events, three additional doses will be administered at 21-day intervals. The 3 week dosing interval may be adjusted based on emerging data from the study, e.g., PK and receptor (GITR) availability. Subjects will also be monitored for anti-drug antibodies (ADA).

##### **4.2.2.4.2 MK-1248 in Combination with Pembrolizumab**

As described previously, the combination of the anti-mouse GITR and anti-mouse PD-1 surrogate antibodies for MK-1248 and pembrolizumab showed greater efficacy in preclinical studies than either agent alone. Therefore, the combination of MK-1248 and pembrolizumab is planned for study in clinical trials to assess whether selected groups of patients with cancer may also derive greater benefit from the combination. As an initial step in testing the combination in clinical trials, this study will assess the safety and tolerability of the combination of MK-1248 and pembrolizumab, and determine a recommended Phase 2 dose for MK-1248 when used in combination with pembrolizumab. Similar to the preclinical studies, MK-1248 and pembrolizumab will be administered on the same day for the first 4 cycles in Arm 2 when both drugs are administered, followed by administration of pembrolizumab alone every 3 weeks for a total of 24 weeks or until a discontinuation criterion is met.

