## 1.0 TRIAL SUMMARY

Abbreviated Title	Phase 1 Trial of MK-1248 as Monotherapy and in Combination with Pembrolizumab in Subjects with Advanced Solid Tumors
Trial Phase	Phase 1
Clinical Indication	Treatment of subjects with advanced solid tumors
Trial Type	Interventional
Type of control	None
Route of administration	Intravenous
Trial Blinding	Unblinded Open-label
Treatment Groups	Subjects will be allocated by non-random assignment to one of 2 treatment arms: Arm 1: MK-1248 as monotherapy Arm 2: MK-1248 in combination with pembrolizumab
Number of trial subjects	Approximately 96 subjects will be enrolled.
Estimated duration of trial	The sponsor estimates that the trial will require approximately 4 years from the time the first subject signs the informed consent until the last subject's last visit.
Duration of Participation	Each subject will participate in the trial from the time the subject signs the Informed Consent Form (ICF) through the final contact. After a screening phase of up to 28 days, each subject will be allocated by non-random assignment into one of two arms and receive treatment with MK-1248 alone or in combination with pembrolizumab. Study treatment in both arms will begin on Day 1 of each 3-week cycle. For subjects enrolled in Arm 1 and Arm 2, treatment with MK-1248 will end after 4 cycles; treatment with pembrolizumab in Arm 2 will continue for up to 24 months. Treatment in both arms will continue until disease progression, unacceptable adverse event(s), intercurrent illness that prevents further administration of treatment, Investigators decision to withdraw treatment, subject withdraws consent, pregnancy of the subject, noncompliance with study treatment or procedure requirements, subject completes treatment, or administrative reasons requiring cessation of treatment. After the end of treatment, each subject will be followed for 30 days for adverse event monitoring (serious adverse events will be collected for 90 days after the end of treatment, or 30 days after the end of treatment if the subject initiates new anticancer therapy, whichever is earlier).

Enrollment into this study has been prematurely discontinued due to program prioritization and not related to any safety concerns. The cut-off date for enrollment is 31-Mar-2017.

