##### **7.1.8.2 Treatment Period**

Visit requirements are outlined in Section 6.0 - Trial Flow Chart. Specific procedure-related details are provided above in Section 7.1 - Trial Procedures.

After a screening phase of up to 28 days, eligible subject will be assigned to one of 2 Arms and a dose level of MK-1248 by IVRS. In Arms 1 and 2, MK-1248 treatment will be administered on Day 1 of each 21-day cycle for up to a maximum of 4 cycles. In Arm 2, pembrolizumab will be administered on Day 1 of each 21 day cycle for up to 24 months of treatment.

Subjects will be followed until confirmed disease progression, unacceptable adverse event(s), intercurrent illness that prevents further administration of treatment, investigator's decision

to withdraw the subject, subject withdraws consent, pregnancy of the subject, noncompliance with study treatment or procedure requirements, or administrative reasons.

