### **8.9 Sample Size and Power Calculations**

#### **8.9.1 Dose Escalation and Dose Confirmation**

The primary purpose of the dose escalation and dose confirmation parts of the trial is to investigate the safety and tolerability of MK-1248 monotherapy and MK-1248 co-administered with pembrolizumab in adult subjects with advanced solid tumors (Parts A-E) and to establish RP2Ds for MK-1248 monotherapy and MK-1248 co-administered with pembrolizumab.

The final number of subjects enrolled in the dose escalation and confirmation parts of the study will depend on the empirical safety (DLT) observations, in particular, at what dose the 3+3 design is triggered and what dose is identified as the RP2D. Sample sizes for a few possible scenarios as well as the estimated time required to enroll all subjects and the time

required to determine the MTD are provided below. The time required to estimate the MTD is the time from the first subject's first dose to the end of the 3-week observation period following the first dose of the last subject enrolled in the dose confirmation part. The study duration is derived as the time from the first subject's first dose to the end of 2-year treatment period following the enrollment of the last Part E subject.

The enrollment time was conservatively estimated assuming that during dose acceleration part it will take 4 weeks to proceed from one dose to the next and during 3+3 parts and that during the dose confirmation a subject can be enrolled every week.

Scenario 1. No DLTs during Parts A-E. For MK-1248 monotherapy, in a scenario where no DLTs are encountered during the dose escalation and confirmation parts and thus Part B continues to the highest dose in [Table 2](#), the sample size across Parts A-C is 46 subjects (8 subjects in Part A, 27 subjects across 9 doses in Part B, and 11 subjects on RP2D in Part C). For MK-1248 with pembrolizumab, in a scenario where Arm 2 starts at 0.12mg MK-1248 and 200 mg pembrolizumab and no DLTs are encountered during the dose escalation and confirmation parts so that Part D continues to the highest dose in [Table 2](#), the sample size across Parts D and E is 50 subjects (39 subjects across 13 doses in Part D, and 11 subjects on RP2D in Part E). The total sample size across Parts A-E is 96 subjects.

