It will take 16 weeks to enroll and observe for DLTs the 8 MK-1248 monotherapy subjects in Part A and proceed to Part B enrolment; it will take additional 88 weeks to enroll 88 subjects (38 in Parts B and C and 50 in Parts D and E). Thus, in this scenario the enrollment time across Parts A-E is 104 weeks and the time required to determine the two MTDs is 107 weeks. The study duration then is approximately 104 weeks + 2 years or 4.0 years.

If dose escalation stops at a dose below the highest dose for either arm, the study might require less than 96 subjects and the enrollment duration shorter than 120 weeks. For example, if, in absence of DLTs, it is decided based on >95% receptor occupancy in tissue samples for multiple consecutive dose levels to stop MK-1248 escalation at 330mg dose and not explore the top three MK-1248 doses in Parts B and D, the sample size across Parts A-E will be 96-18=78 subjects. The enrollment duration will be 104-18=86 weeks and the total study duration will be 86 weeks+2 years or 3.6 years.

Also, with no DLTs observed, it might be possible to enter Part C and Part E subjects faster than one subject every week which will shorten the study duration.

Scenario 2: Flat DLT dose response. Suppose no DLTs are observed in Part A, and dose escalation in Parts B and D continues to the highest dose with flat dose response so that in Arm 1, 4 dose levels are studied in 3 subjects each and 5 dose levels (including the top one) are studied in 6 subjects each in Part B, while in Arm 2, 6 dose levels are studied in 3 subjects each and 7 dose levels (including the top one) are studied in 6 subjects each in Part D. Also suppose that the top dose is confirmed as the RP2D dose without de-escalation in Parts C and E. Thus, the sample size in Arm 1 is 58 subjects (8 in Part A, 42 in Part B, and 8 in Part C) and the sample size in Arm 2 is 68 subjects (60 in Part D and 8 in Part E). Total sample size is 118 subjects.

It will take 16 weeks to enroll 8 MK-1248 monotherapy subjects in Part A and proceed to Part B enrolment; it will take additional 118 weeks to enroll 118 subjects (50 in Parts B and C, and 68 in Parts D and E). Thus, in this scenario the enrollment time across parts A-E is

134 weeks and the time required to determine the two MTDs is 137 weeks. The study duration then is approximately 137 weeks + 2 years or 4.6 years.

Any dose de-escalations in Part C will increase the sample size in this example.

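### The protocol gives two maximum durations for pembrolizumab in Arm 2, 24 weeks in Section 4.2.2.4.2 and 24 months (2 years) in Sections 1.0, 7.1.8.2 and 8.9.1, so completion of treatment has no single definition

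*Combined protocol and SAP*

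**What the plan says.** Section 4.2.2.4.2 sets out the Arm 2 regimen. MK-1248 and pembrolizumab are given on the same day for four cycles, "followed by administration of pembrolizumab alone every 3 weeks for a total of 24 weeks or until a discontinuation criterion is met".

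Three other sections give a different length:

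- Section 1.0, Duration of Participation: "treatment with pembrolizumab in Arm 2 will continue for up to 24 months".
- Section 7.1.8.2: "In Arm 2, pembrolizumab will be administered on Day 1 of each 21 day cycle for up to 24 months of treatment".
- Section 8.9.1, which runs study duration "to the end of 2-year treatment period following the enrollment of the last Part E subject" and then, for Scenario 1, states: "The study duration then is approximately 104 weeks + 2 years or 4.0 years". The other scenarios also add 2 years.

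The flow chart in Section 6.0 has an open-ended Arm 2 column from Cycle 7 onward. Its footnotes 20 and 21 schedule pembrolizumab antibody and PK samples before dosing in Cycles 5, 6 and 8 and at every fourth cycle after that. Table 3 in Section 5.2 gives dose, frequency and dosing day but no duration, so it does not settle the matter.

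**The concern.** Section 4.2.2.4.2 is current text and says how subjects in this trial will be treated. It is not preclinical background or a record of superseded wording. Neither way of reading its 24 weeks gives 24 months.

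The length of treatment has a practical role. Section 5.8 lists completion of treatment as the protocol defines it among the reasons for which a subject must stop. It also says that stopping is permanent and that treatment may not be restarted. The protocol therefore ties a mandatory, irreversible step to a point it defines in two ways.

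The question is still live. Enrollment closed on 31-Mar-2017, but Section 1.0 lets ongoing subjects continue study treatment per protocol. Those in Arm 2 who have not progressed or stopped for another reason are the ones affected. The safety visit and the adverse event, serious event and pregnancy reporting periods all run from the last dose or from cessation of treatment (Sections 7.1.8.3.1, 7.2, 7.2.2, 7.2.3.1 and 7.2.3.2). Their calendar dates would therefore move with the end of treatment.

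**Working it through.** **Inputs.** Dosing interval of 3 weeks and 200 mg per dose (Section 4.2.2.2: "The planned dose of pembrolizumab for this study is 200 mg given once every 3 weeks"); four combination cycles, or 12 weeks (Section 1.0); 24 weeks (Section 4.2.2.4.2); 24 months, taken as 104 weeks (Sections 1.0 and 7.1.8.2).

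**The plan's own duration figure.** Scenario 1 enrollment is 16 weeks for Part A, 38 for Parts B and C and 50 for Parts D and E: 16 + 38 + 50 = 104 weeks. At 52.18 weeks per year, 104 / 52.18 + 2 = 3.99 years, which reproduces the stated 4.0 and agrees with the estimate of about 4 years in Section 1.0. The same sum with the other durations gives:

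- 24 weeks in total: (104 + 24) / 52.18 = 2.45 years.
- 12 + 24 = 36 weeks in total: (104 + 36) / 52.18 = 2.68 years.

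Only the 2-year period gives 4.0 years.

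**Maximum number of doses** = weeks / 3, rounded up because dosing is on Day 1 of each cycle. The last Day 1 falls at week 3 × (doses − 1).

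| Reading | Weeks | Doses | Total mg | Last dose at week |
|---|---|---|---|---|
| 24 weeks in total | 24 | 8 | 1600 | 21 |
| 24 weeks after the four combination cycles | 36 | 12 | 2400 | 33 |
| 24 months | 104 | 35 | 7000 | 102 |

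Ratios of maximum doses: 35 / 8 = 4.4 and 35 / 12 = 2.9. Comparing only the pembrolizumab-alone phase, (104 − 12) / 24 = 92 / 24 = 3.8.

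**Shift in the end of treatment** for a subject who reaches the ceiling: 102 − 21 = 81 weeks, or 102 − 33 = 69 weeks.

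**Flow chart.** Cycle 8 Day 1 is at week 21, Cycle 12 at week 33 and Cycle 16 at week 45. If 24 weeks is the total, no pre-dose sample after Cycle 8 could be taken. If the total is 36 weeks, Cycle 12 would be the only one, which fits poorly with an open-ended rule of every fourth cycle.

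**The case against.** The case for treating this as minor is that the 24-week figure is one clause in a rationale section. The Trial Summary, the Treatment Period section, the flow chart and the duration calculation are all compatible with 24 months. The number is 24 throughout and only the unit differs, so a drafting slip is plausible. A site working from Section 7.1.8.2 and the flow chart would see one duration. That is fair as to how the conflict probably arose. But the clause says what subjects will receive, the protocol gives no order of precedence between sections, and the documents do not say which figure was meant.

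Much of the rest of the objection stands, and it limits what can be claimed. A reader might infer four stronger points that the documents do not support:

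- **A four-fold difference in exposure.** The ratio of total doses is 4.4 or 2.9, depending on how 24 weeks is read. Both durations are ceilings: treatment also ends at progression, unacceptable toxicity or other criteria. The ratio does not describe expected exposure.
- **Changed analyses.** Extent of exposure (Section 8.12) counts doses actually received. Pembrolizumab compliance (Section 8.11) uses the actual first and last dose dates. Database lock (Section 8.2) is tied to 6 months after first dose. The DLT endpoint is confined to Cycle 1. None of these derivations uses the planned duration.
- **Different lengths of reporting window.** The lengths are the same under either text. Only the start dates move, and only if a site acts on Section 4.2.2.4.2.
- **A wrong study duration.** Section 8.9.1 uses 2 years consistently and never takes 24 weeks as an input. The figures of 2.45 and 2.68 years show what would follow from the other text; they are not an error in the stated 4.0.

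**Conclusion.** The contradiction is real and should be corrected. Its size is about 35 maximum doses against 8 or 12, a ratio of about 4.4 or 2.9. For a subject who stays on treatment to the ceiling, the last dose would differ by 81 or 69 weeks. This assumes dosing every 3 weeks without delay and 24 months taken as 104 weeks. The choice between 8 and 12 doses depends on wording in Section 4.2.2.4.2 that can be read either way.

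The consequence is operational. Two sites could each follow the protocol and still stop treatment, and start post-treatment safety and follow-up, at different times. The primary endpoint, N = 96 and the exposure and compliance derivations are unaffected, and the 4.0-year study duration is consistent only with the 2-year period. This is an internal inconsistency, not a questionable design choice. This review takes no position on which duration is clinically right.

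**What to change.** Reconcile Section 4.2.2.4.2 with Sections 1.0, 7.1.8.2 and 8.9.1 so that one maximum pembrolizumab duration is stated, and say whether it includes the four combination cycles. Check that the flow-chart sampling after Cycle 8 fits the duration stated.

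The study-duration figures in Section 8.9.1 and the 4-year estimate in Section 1.0 need revision only if the reconciled duration differs from the 2 years they already use. The edit to Section 4.2.2.4.2 is one line in the next amendment. No analysis or sample-size work is needed.
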